This part will be a single cohort, randomized, open-label, 2-period, crossover design, randomizing 8 (minimum) to 12 (maximum) participants who will receive PF-07202954 once with a high-fat/high-caloric meal and once following an overnight fast of ≥ 10 hours with the order randomly assigned. Since the dose in this part (refer to [Section 4.3.5](#)) will be selected based on observed safety, tolerability, and PK of single doses in Part 1 and the dose selected will be lower than the highest dose tested in Part 1, standard safety monitoring will be used in this part of the study.

4.2.5. Rationale for Dosing with Standard Meal in Part 1 and Part 2

In Part 1 and Part 2 of this study, PF-07202954 will be administered with a standard morning meal because PF-07202954 is expected to be administered with food in clinical practice and administration with a meal helps in the assessment of the effect of PF-07202954 [REDACTED]

[REDACTED] Although food is expected to have minimal impact on PF-07202954 exposures at doses ≤ 1500 mg based on the physical and chemical properties of PF-07202954 and simulations of a PBPK model, the effect of a high-fat/high-caloric meal on plasma concentrations of PF-07202954 may be evaluated in Part 1 and/or Part 3 of this study.

CC1 [REDACTED]

[REDACTED]

[REDACTED]

[REDACTED]

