#### Mixed Effect Analysis of Variance (ANOVA)

The mixed effect ANOVA model will be used to assess the food effect in Part 1 or Part 3, **CCI** For endpoints in Part 1 of the study treatment group will be the fixed effect and participant will be the random effect. In Part 3, sequence, period and treatment will be the fixed effects and participant within sequence will be the random effect. Estimates of treatment effects will be assessed using the least square means (LSMs) and 80% Confidence Intervals (CIs). Estimates of the mean differences between each active dose and placebo, and the corresponding 80% CI will be obtained from the model. If there are major deviations from the statistical assumptions underlying this model then non-parametric analyses may be presented.

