### 6.1. Primary Endpoint(s)

The primary endpoints in Part 1 and Part 2 are related to safety/tolerability whose analyses are described Section 6.6.

The primary endpoints in Part 3 are the plasma PK endpoints whose analyses are described in Section 6.2.

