**TABLE 8. URINE PK PARAMETERS TO BE SUMMARIZED DESCRIPTIVELY**

Parameter	Summary Statistics
Ae tau , Ae tau % and CL r	N, arithmetic mean, median, %CV, SD, min, max, geometric mean and geometric %CV.

- **Part 1 (Single, Escalating Doses):**
- Plasma concentrations of PF-07202954 will be descriptively summarized and plotted by nominal PK sampling time and dose.

- The plasma PK parameters  $AUC_{inf}$ ,  $C_{max}$ ,  $AUC_{last}$ ,  $T_{max}$ ,  $T_{lag}$ ,  $CL/F$ ,  $V_z/F$ , and  $t_{1/2}$  will be summarized descriptively by dose;

[REDACTED]

[REDACTED]

- **Part 2 (Repeated, Escalating Doses):**

- Plasma concentrations of PF-07202954 will be descriptively summarized and plotted by nominal PK sampling time, day, and dose;
- The plasma PK parameters  $AUC_{tau}$ ,  $C_{max}$ ,  $T_{max}$ ,  $T_{lag}$ ,  $t_{1/2}$ ,  $C_{min}$ ,  $C_{av}$ ,  $PTR$ ,  $CL/F$ ,  $V_z/F$ ,  $R_{ac,AUC_{tau}}$ , and  $R_{ac,Cmax}$ , and the urine PK parameters  $Ae_{tau}$ ,  $Ae_{tau}\%$ , and  $CL_r$  will be summarized descriptively by dose and day as applicable;

[figure not shown]
[figure not shown]
[REDACTED]

- Median morning trough (predose) plasma concentrations will be plotted by day (all doses on the same plot) in order to assess the attainment of steady state.
- **Part 3 (Single-Dose Food Effect, if conducted):** To compare PF-07202954 exposures following high-fat/high-caloric meal (Test) versus following an overnight fast (Reference) natural log-transformed  $C_{max}$ ,  $AUC_{last}$ , and  $AUC_{inf}$  (if data permit) will be analyzed using a mixed effects ANOVA described in Section 5.2. Estimates of the adjusted mean differences (Test-Reference) and the corresponding 90% CIs will be obtained from the model. The adjusted mean differences and 90% CIs for the differences will be exponentiated to provide estimates of the ratio of adjusted geometric means (Test/Reference) and 90% CIs for the ratios.

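### Does the 80% confidence level in the SAP 5.2 mixed-effect ANOVA paragraph put the 90% intervals planned for the Part 3 food effect in doubt?

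*SAP*

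**What the plan says.** SAP 5.2, under General Methods, describes a mixed-effect ANOVA. Its first sentence gives the use: "The mixed effect ANOVA model will be used to assess the food effect in Part 1 or Part 3", followed by a blacked-out continuation. It then gives model terms separately for Part 1 and for Part 3; for the latter, "In Part 3, sequence, period and treatment will be the fixed effects and participant within sequence will be the random effect". Two sentences on estimation follow. One reads "Estimates of treatment effects will be assessed using the least square means (LSMs) and 80% Confidence Intervals (CIs"). The other reads "Estimates of the mean differences between each active dose and placebo, and the corresponding 80% CI will be obtained from the model". The visible text makes no exception for Part 3.

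SAP 6.1 states: "The primary endpoints in Part 3 are the plasma PK endpoints whose analyses are described in Section 6.2". In SAP 6.2 the log-transformed Cmax, AUClast and AUCinf from Part 3 "will be analyzed using a mixed effects ANOVA described in Section 5.2". The instruction there is: "Estimates of the adjusted mean differences (Test-Reference) and the corresponding 90% CIs will be obtained from the model". The differences and their 90% limits are then exponentiated to give fed/fasted ratios of geometric means.

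Protocol 9.4.3.2 gives the same contrast, the same back-transformation and the same 90% level. Protocol 9.2, Table 6, sizes Part 3 on probable 90% intervals with 80% coverage probability. SAP 5.1 states that the study has no hypotheses or decision rules.

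**The concern.** Plasma PK is the primary endpoint of Part 3, and the paragraph that defines its model carries a different confidence level from the section that reports its result. It also describes a comparison that cannot be made in Part 3. Protocol 4.2.4 describes "participants who will receive PF-07202954 once with a high-fat/high-caloric meal and once following an overnight fast", so nobody in Part 3 receives placebo.

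The paragraph cannot be set aside as having nothing to do with Part 3, since it names Part 3 and gives its fixed and random effects. SAP 6.2 does not repeat those terms, so whoever builds the model must open 5.2 and will meet the 80% there. If that level were carried to the ratio, the food effect would be shown with a tighter interval than the one used to size Part 3. The smallest permitted sample would then look about as precise as the largest does in Table 6.

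**Working it through.** **1. Reproduce Table 6, to see which level the sizing rests on.** Inputs from Protocol 9.2: n = 8, 10, 12; within-participant SD on the log scale 0.18, 0.21, 0.24; true ratio 1.0; 90% interval; 80% coverage probability. With sequence, period and treatment fitted in a two-period crossover (SAP 5.2), the error degrees of freedom are n − 2. The limits are

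exp(± t × SD × √(2/n) × √(χ²(0.80, n−2)/(n−2))), where t is the 0.95 quantile on n − 2 df for a 90% interval and the 0.90 quantile for an 80% interval.

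Worked cell, n = 8 and SD = 0.24 at 90%: t = 1.943; √(2/8) = 0.500; coverage factor 1.194. The half-width is 1.943 × 0.24 × 0.500 × 1.194 = 0.278, giving limits of 0.76 and 1.32, as in Table 6.

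All nine cells match to two decimals. With an 80% interval in the same formula none match, and the largest difference is 0.09. The sizing therefore rests on 90%.

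**2. Size of the difference if 80% were used for the ratio.** Only the t quantile changes.

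| n | t at 90% | t at 80% | Ratio | Limits at SD 0.24, 90% (Table 6) | Limits at SD 0.24, 80% |
|---|---|---|---|---|---|
| 8 | 1.943 | 1.440 | 0.741 | 0.76–1.32 | 0.81–1.23 |
| 10 | 1.860 | 1.397 | 0.751 | 0.79–1.26 | 0.84–1.19 |
| 12 | 1.812 | 1.372 | 0.757 | 0.81–1.23 | 0.86–1.17 |

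On the log scale the interval would be 26%, 25% and 24% narrower. At SD 0.24 the log half-width for n = 8 at 80% is 0.2063, against 0.2059 for n = 12 at 90%, which is the apparent gain in precision described above.

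**3. Whether a reader of the plan could arrive at 80% for the ratio.** What each section supplies for Part 3:

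| Item | SAP 5.2 | SAP 6.2 |
|---|---|---|
| Model terms | Yes | By reference to 5.2 |
| PK endpoints | No | Cmax, AUClast, AUCinf |
| Log transformation | No | Yes |
| Fed-minus-fasted contrast | No | Yes, 90% |
| Ratio of geometric means | No | Yes, 90% |
| Active-minus-placebo contrast | Yes, 80% | No |
| Least squares means and treatment effects in general | Yes, 80% | Not given a level |

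The sentence in 5.2 that puts 80% on a difference ties it to placebo. No sentence there puts 80% on a fed-minus-fasted difference or on a ratio. The ratio is defined only in 6.2, where 90% is stated with it, so the output cannot be specified without reading the intended level.

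**4. Why the placebo wording is there.** The same two 80% sentences stand under ANCOVA in SAP 5.2. Part 1 is a placebo-controlled crossover (Protocol 4.2.2 and Table 5), so an active-minus-placebo contrast is valid for Part 1 endpoints under this model. The paragraph is shared text serving more than one use, and part of its list of uses is blacked out.

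**The case for a change.** The best argument for acting is that a SAP should not give two levels for one model when the endpoint is primary. The phrase about treatment effects in 5.2 is unqualified and can be read to include the food effect. The SAP also says it may modify the protocol, so a level that departs from the protocol is not obviously a slip. A short cross-reference would settle the matter at almost no cost.

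Part of this stands. The visible wording of 5.2 is imprecise, and a pointer to 6.2 would be tidier. But the possible modification of the protocol does not help the argument, because the SAP's own endpoint section repeats the protocol's 90%. A general-methods paragraph gives way to the section written for the endpoint, and SAP 6.1 directs the reader to that section. A pointer would leave the estimate, interval, sample size and reported result of Part 3 as they are. A broader edit that reserved 80% and placebo contrasts for every other use of the model could do harm: it could be read to fix the level for the exploratory Part 1 food-effect look, and it would set rules for uses that are blacked out.

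**Conclusion.** This is a drafting looseness in a shared methods paragraph, and no change to the plan is needed. SAP 6.2, Protocol 9.4.3.2 and Table 6 all lead to fed/fasted ratios with 90% intervals, and an analyst following SAP 6.1 and 6.2 would report them. The 24% to 26% narrowing describes a misreading, not the plan. Even then no stated decision would turn on it, given SAP 5.1, and Part 3 itself is conditional.

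Two assumptions underlie this. The first is that endpoint-specific text governs over general text within one SAP. The second is that the blacked-out words after the mention of Part 3 in SAP 5.2, and the blacked-out part of SAP section 6, do not assign another level to the Part 3 ratio; nothing visible suggests that they do. Nothing is concluded here about the level for a Part 1 food-effect comparison.

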### **Analysis of Covariance (ANCOVA)**

The ANCOVA model will be used with continuous endpoints for landmark (single time point) analyses. The model will include treatment group as a fixed effect, baseline value of the endpoint being analyzed as a covariate. Study site and interaction of study site with treatment will be considered to be included as potential covariates for the analysis of whole liver fat only. Estimates of treatment effects will be assessed using the least square means (LSMs) and 80% Confidence Intervals (CIs). Estimates of the mean differences between each active dose and placebo, and the corresponding 80% CI will be obtained from the model. If there are major deviations from the statistical assumptions underlying this model then alternative transformations or non-parametric analyses may be presented. Justification for any alternative to the planned analysis will be given in the study report.

### **Mixed Model for Repeated Measurements (MMRM)**

This model will be used for the analysis of endpoints with more than one post-baseline collection time point. All observed data collected during the post-baseline treatment period up to and including 1st Follow-up visit (conducted onsite) in Part 2 will be utilized; data collected during the follow-up period will be excluded. Early discontinuation data will also be excluded. The MMRM analysis will be performed with treatment, study day and treatment-by-study day interaction as fixed effects, baseline value as a covariate. Repeated measures model with unstructured correlation matrix will be utilized. Time will be fitted as a repeated effect. If this does not converge then compound symmetry structure will be considered. Estimates of treatment effects will be assessed using LSMs and 80% CIs at each time point. LSM difference between each dose of PF-07202954 and placebo group along with the 80% CIs and 2-sided p-values will be provided. If there are major deviations from the statistical assumptions underlying this model then alternative transformations (e.g. log) or non-parametric analyses may be presented. Justification for any alternative to the planned analysis will be given in the study report.

### **Non-parametric Analysis**

If the data have many outliers even after the log-transformation the following non-parametric analysis will be performed instead of the linear model. An outlier will be defined as any datapoint falling outside of  $3.5 \times$  standard deviations +/- the median. Additional evaluative

statistics will be conducted to explore the nature of the outliers in order to determine the appropriateness of a parametric analysis.

For group medians 80% CIs will be presented. In addition, the 80% CIs will also be presented for differences in group medians from placebo group median. The method of McGill, Tukey, and Larson will be employed to calculate the CI for the difference in treatment group medians.

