Given the current study is the first time PF-07202954 will be administered to humans, an escalating single oral dose design is planned with careful assessment and ongoing review of safety data and PK of PF-07202954. Part 1 is designed as a randomized, dose -escalating, cross-over, interleaving, placebo-controlled, 2-cohort, study with dosing of study intervention (PF-07202954/placebo) planned following ≥ 10 hours overnight fast, at approximately 8:00AM (± 2 hours) to occur **with** standard morning meal provided ~ 30 mins

prior to dosing at 0H. By design, at each dose level, 6 participants are planned to receive PF-07202954 and 2 participants are planned to receive placebo with all participants at the end of Part 1 having received 1 dose of placebo and up to 3 *unique* doses of PF-07202954. The rationale for selection of the starting (ie, first) dose level in Part 1 is outlined in [Section 4.3.3](#). In addition, the highest anticipated steady-state AUC₂₄ and C_{max} for PF-07202954 in Part 1 will *not* exceed the pre-identified stopping exposure limit determined based on nonclinical toxicity study (refer to [Section 6.6.1](#)) *nor* exceed the highest feasible total daily dose of 2000 mg.

The design of Part 1 permits both a within and between participant assessment of safety/tolerability and dose-response for PK and exploration of effect on plasma PCSK9. Furthermore, to permit an unbiased assessment of safety, the administration of active versus placebo in each Period will be double-blinded to both site staff (except those involved in preparation of doses) as well as the participants. However, to permit real-time review of the safety and PK data, the sponsor will be unblinded, although measures to limit degree of unblinding will be exercised – refer to [Section 9.5](#) for details. In light of the findings in the 6 week toxicity studies in rats and monkeys, the safety assessments envisioned in this study administrating investigational product for the first time to humans are outlined in [Section 8.2](#).

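### In the Part 1 crossover, the SAP's non-parametric fallback drops the within-participant pairing; the loss of precision depends on a correlation that the documents do not give

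*SAP*

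**What the plan says.** For Part 1, the mixed-effect ANOVA subsection of SAP 5.2 keeps the pairing: "For endpoints in Part 1 of the study treatment group will be the fixed effect and participant will be the random effect". Each active dose is contrasted with placebo, with an 80% interval. The subsection then opens a way out: "If there are major deviations from the statistical assumptions underlying this model then non-parametric analyses may be presented".

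The only non-parametric method readable in the SAP is in the Non-parametric Analysis subsection of 5.2. Its trigger and status are: "If the data have many outliers even after the log-transformation the following non-parametric analysis will be performed instead of the linear model". Its outputs are intervals for each group ("For group medians 80% CIs will be presented") and contrasts with placebo ("In addition, the 80% CIs will also be presented for differences in group medians from placebo group median"). The McGill-Tukey-Larsen method "will be employed to calculate the CI for the difference in treatment group medians". The subsection has no separate rule for Part 1 and does not mention within-participant differences.

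Under Protocol 4.2.2, each Part 1 dose level has six participants on active drug and two on placebo, and everyone receives placebo once and up to three active doses. The Protocol presents this as a strength: "The design of Part 1 permits both a within and between participant assessment". The same section pools the placebo data for comparison with each dose, in the context of choosing the next dose.

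**The concern.** The fallback contrast is a difference of two marginal medians. In Part 2 those groups contain different people. In Part 1 every participant in the active group is also in the placebo group. Participant-to-participant variation, which the mixed model removes, therefore returns to the comparison. An interval built from each group's own spread and size does not respond to the overlap. If the fallback were applied to raw Part 1 values, the study would give up the comparison that the crossover was designed to provide, in the very cases where the linear model had been set aside.

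**Working it through.** The documents state no width, coverage or correlation for this fallback, so there is no figure of theirs to reproduce.

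**1. Counts (Protocol Table 5).** Each dose appears in three of its cohort's four sequences, with two participants each: 3 × 2 = 6 active values. Placebo appears once in each of eight sequences: 8 × 2 = 16 placebo values. All six active participants are among the 16.

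**2. Approximation.** Treat medians like means, with unit variance and within-participant correlation ρ (assumed).
- Variance if the groups are taken as independent: 1/6 + 1/16 = 0.229
- Variance allowing for the six shared participants: 0.229 − 2ρ/16
- Variance from six paired differences: 2(1 − ρ)/6

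At ρ = 0.8 the independence assumption overstates the standard error by √(0.229/0.129) = 1.33, and the ratio to the paired standard error is √(0.229/0.0667) = 1.85. The independence and paired variances are equal when (1 − ρ)/3 = 0.229, which gives ρ = 0.31. At ρ = 0.5 the second and third variances are both 0.167. On this approximation the two estimates are then equally precise, and the excess width (1.17) comes only from ignoring the overlap.

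**3. Simulation.** The SAP cites its method without printing a formula. The working assumption is a standard error for each group median of 1.25 × IQR/(1.35√n), combined as a root sum of squares and multiplied by 1.282. The comparator is the signed-rank interval on six active-minus-own-placebo differences. Seven of the 64 sign patterns fall in each tail, so its exact level is 1 − 14/64 = 78.1%. The next level up is 1 − 10/64 = 84.4%.

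Normal errors, 16 placebo values, linear-interpolation quartiles, 100,000 trials per setting, full widths in SD units:

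| ρ | Fallback width | Paired 78% width | Ratio | Fallback coverage |
|---|---|---|---|---|
| 0 | 1.304 | 1.573 | 0.83 | 73% |
| 0.3 | 1.305 | 1.320 | 0.99 | 77% |
| 0.5 | 1.302 | 1.113 | 1.17 | 79% |
| 0.7 | 1.297 | 0.863 | 1.50 | 81% |
| 0.8 | 1.297 | 0.706 | 1.84 | 83% |
| 0.9 | 1.295 | 0.498 | 2.60 | 86% |

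The fallback width barely moves with ρ, while the paired interval narrows and stays at about 78% coverage.

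**4. Other quartile rule and heavier tails (40,000 trials per setting).** With averaged quartiles, the half-widths at ρ = 0.7 with normal errors are 0.754 against 0.432, a ratio of 1.75 with 87% coverage. At ρ = 0.85 with t errors on 3 degrees of freedom they are 0.739 against 0.279, a ratio of 2.65 with 90% coverage.

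Over ρ = 0.5 to 0.85 the ratio therefore runs from about 1.2 to 2.7 and coverage from about 79% to 90%. The standard deviation of the fallback estimate was 1.16 to 2.16 times that of the paired estimate.

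**5. Own-cohort placebo only (8 values).** With the settings of step 3, coverage is 82% at ρ = 0.5 and 90% at 0.8.

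**The case against.** **Reach.** The route from the Part 1 model is discretionary, and parts of the SAP that define and analyse the tertiary endpoints are redacted. A Part 1 rule could sit there, so a reader should not infer that the plan has no paired version anywhere. This stands, and the point is confined to the readable general method.

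**Baseline.** SAP Table 2 defines the Part 1 baseline for non-PK endpoints as time-matched placebo data. For an endpoint expressed as change from that baseline, pairing is already built in and the criticism lapses. But the placebo change is then zero by definition, and a further difference from the placebo median has no meaning. The wording still does not fit Part 1.

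**Size.** Against the 84% paired interval at ρ = 0.5 with linear quartiles, the width ratio is only 0.99. At ρ = 0 the paired interval is the wider one, because it uses 6 of the 16 placebo values. Pairing is not always better.

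**Coverage.** A reader might infer that the stated 80% intervals are simply invalid. The figures do not support that. With pooled placebo and ρ of 0.5 or more, departures are mostly conservative. Near ρ = 0.5 two errors offset each other, since under linear quartiles the same interval covers only about 73% for truly independent groups. The paired alternative is itself at 78% or 84%. Uncontrolled coverage is the fair description.

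**Trigger.** An outlier must lie more than 3.5 standard deviations from the median. With k equal outliers on one side and all other values at the median, the distance is √[(n − 1)/(k(1 − k/n))] standard deviations. For n = 6 and k = 1 this is 2.45, so no value in a six-participant group can qualify. For 64 pooled values (16 participants × 4 periods) it is 3.70 at k = 5 and 3.40 at k = 6, so at most five can. The fallback would seldom be triggered by outliers.

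**Conclusion.** The point holds in limited form. The SAP's readable fallback is unpaired, has no Part 1 exception, and does not match the crossover. The firmer harm is lost precision when within-participant correlation is moderate or high. The 1.2 to 2.7 width ratio and the 79% to 90% coverage rest on an assumed correlation of 0.5 to 0.85, 16 pooled placebo values and the assumed standard-error formula. At or below about 0.3 there is little or no gain in width from pairing.

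A reader might also infer that dose escalation or the possible interim analysis depends on this. SAP 7.2 does apply the SAP's methods to Part 1 data, but the endpoints that could reach the fallback are largely redacted, so that link cannot be shown. SAP 5.1 sets no hypotheses or decision rules, 6.2 applies no formal inference to Part 1 and Part 2 plasma PK, and 6.6 plans no formal analysis of standard safety data. Severity is low.

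**What to change.** Add to the Non-parametric Analysis subsection of SAP 5.2:
- **Part 1 endpoints analysed as raw values:** the Hodges-Lehmann estimate of active minus own placebo, on the log scale where that scale is used, with the exact signed-rank interval nearest 80%. State in advance whether that is the 78% or the 84% level with six pairs.
- **Part 1 endpoints already defined as change from time-matched placebo:** the one-sample version, with no further placebo contrast.
- **Group-median method:** Part 2 only. This also keeps it away from the food-effect comparison that the mixed ANOVA covers, where a contrast with a placebo median would not apply.

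The cost is a few sentences and standard code. The downsides are that the level is not exactly 80%, that the 10 placebo values (16 − 6) from participants not on that dose go unused, and that a participant without a placebo period drops out of the contrast.
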